# SPECIFIC AIMS

**Primary:** To compare IN-OXT vs. placebo on changes on the Hyperphagia Questionnaire-Clinical Trials (HQ-CT) from baseline to week 8 in children with PWS. We hypothesize that IN-OXT will be significantly superior to placebo in improving hyperphagia.

Secondary: To compare the change from baseline to week-8 of IN-OXT vs. placebo on:

- 1. Repetitive Behavior Scale-Revised (RBS-R).
  - We hypothesize that IN-OXT will significantly reduce repetitive behaviors from baseline to endpoint as measured by a reduction of the score on the RBS-R when compared to placebo.
  - We hypothesize that IN-OXT will significantly reduce rigid behaviors from baseline to endpoint as measured by a reduction of the score on the MERS-PWS when compared to placebo.
- 2. Weight, BMI (z-score) and Body composition via bioelectrical impedance analysis
  - We hypothesize that IN-OXT will significantly reduce weight and BMI compared to placebo.
  - We hypothesize that IN-OXT will significantly reduce body fat compared to placebo, as measured by body composition via bioelectrical impedance analysis.
- 3. Quality of Life Measures
  - We hypothesize that IN-OXT will improve quality of life measured by an increase in overall score on the WHOQOL from baseline to endpoint when compared to placebo.
  - We hypothesize that IN-OXT will improve quality of life measured by a reduction in overall score on the CSQ from baseline to endpoint when compared to placebo.
- 4. Salivary Oxytocin Concentration
  - We hypothesize that higher concentrations of salivary oxytocin will be correlated with positive changes on each outcome measure, indicating improvement in symptoms.
- 5. Safety Analyses
  - We hypothesize that IN-OXT will not increase side-effect burden from baseline to endpoint compared to placebo.

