**Research Strategy And Feasibility:** We propose a three year, phase 2, randomized doubleblinded 8-week treatment trial of IN-OXT vs. placebo in 50 child and adolescent subjects (25 male and 25 female) aged 5 to 17 years with a diagnosis of PWS. PWS diagnosis will be confirmed by study team via patient interview and confirmation by patient's past medical records and genetic testing results. At the screening visit, patient will have the opportunity to learn about the study and seek clarification on any outstanding questions. If patient voluntarily agree to participate, study team will work with the patients to complete the informed consent and if applicable, assent. In addition, a psychiatric interview and medical history review will be conducted to screen the patient for eligibility. The study team will also review patient's concomitant medications, assess for patient condition with CGI-S and hyperphagia using the Hyperphagia Questionnaire-Clinical Trials (HQ-CT). If patient meets selection criteria, the study team will arrange on behalf of the patient for an out-patient Quest visit, at which time patient will be asked for a screening blood draw to provide information on CBC, BMP, LFT, IGF-1, thyroid panel, lipid panel, testosterone, estrogen, hemoglobin A1C, and for applicable patient, a urine pregnancy test. Once the screening blood work results are available and all results are within acceptable range, and patient is otherwise eligible, patient will be invited for an in person visit to clinic where additional assessments including a complete physical and neurological exam, intelligence test, interval health or medication change, and if applicable, repeat urine pregnancy test will be conducted. If patient continues to meet all study inclusion and exclusion criteria and agrees to continue with study participation, the study team will formally submit the patient for randomization. The randomization is done in a 1:1 placebo to oxytocin ratio and stratified for gender. The result is blinded to the study team and the process is performed by the study pharmacist at the Clinical Research Pharmacy using a computer generated randomization table. Patients will receive a supply of oxytocin spray bottle with each spray dispensing 4 IU, or a matching placebo. The participant will start with an initial dose of 2 sprays per nostril (4 sprays per day), or 16 IU/day IN-OXT or placebo. To allow for optimization for adverse events or lack of response, we allow for one downward titration to 12 IU (3 sprays per day), and one upward titration to 24 IU (6 sprays per day) at week 2. This will also allow us to examine the relationship between weight based dosing and treatment response. Syntocinon (synthetic intranasal oxytocin) and matched placebo made by Novartis will be used in this protocol. We have an IND for the use of IN-OXT in PWS (IND 121109).

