The time commitment and study burden is similar to other current studies in this population and the ASD population. If needed, visits can be split into two visits. Parents may prefer to attend a visit by themselves without the child to complete their measures. Visits at screening, weeks 2, 4, 6, and 10 (follow-up) are remote visits done via tele-medicine. The study clinicians will complete the video conference call with the parent. This will further reduce the family's burden and decrease the amount of times they need to travel to the study site. As much flexibility in scheduling as necessary will be given to the patients and families. Reimbursement for time and travel is provided at each visit (\$150 – in-person; \$30 – phone visit). Additional reimbursement for travel will be provided as needed for families traveling long distances. The average time needed for parents, child and clinician to complete the assessments is detailed below. Details about which measures are included in each visit can be seen in **Table 2: Schedule of Events.** Some assessments require the participation of both the parent and child and times reflect how long each individual is needed independent of combined measures. Families may differ in how long it takes them to complete certain measures and the times do not include any breaks for meals or walking between sites at the clinic.

Screening Visit (remote): 3-4 hours Baseline Visit (in-person): 4-5 hours Week 2 and Week 6 (remote): 30 minutes Week 4 (remote): 2-3 hours Week 8 (in-person): 4-5 hours Week 10 Follow Up (remote): 2-3 hours

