#### **PRIMARY OUTCOME:**

**Hyperphagia Questionnaire-Clinical Trials (HQ-CT)**: The Hyperphagia Questionnaire-Clinical Trials (HQ-CT) is the standard for assessing how potential therapies may impact hyperphagia in PWS clinical trials. It is a caregiver-rated assessment comprised of 9-items that measure and track the food seeking behaviors and drive for food that is associated with PWS. The HQ-CT is a modified version of the [name]-Hyperphagia Questionnaire (a well-established questionnaire), with changes based on industry and regulatory standards (e.g., Food and Drug Administration, 2009). These modifications included a reduced recall period, optimization of response scales, and limiting item content to observable behaviors that have the potential to change during the course of a clinical trial. Psychometric evaluation demonstrated the HQ-CT's reliability and validity, and the HQ-CT total score has demonstrated improvements in hyperphagia-related behavior between treatment groups in children with PWS. The HQ-CT will be administered at screening, baseline, and at all subsequent visits. In order to be eligible to participate in the trial, scores on the HQ-CT will need to be at least of moderate severity at both screening and baseline visits. It will take about 15 minutes to complete.

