#### Caregiver Strain Questionnaire (CSQ):

The Caregiver Strain Questionnaire is a well-validated, reliable 21-item measure of selfreported strain experienced by caregivers and families of youth with emotional problems, with responses on a 5-point Likert scale (0 = Not at all, 4 = very much).

**Clinical Global Impression Scale – Improvement (CGI-I):** The CGI-I will be used as a measure of improvement and contains a 7 point scale as follows: 1 = very much improved, 2 = much improved, 3 = minimally improved, 4 = no change, 5 = minimally worse, 6 = much worse, 7 = very much worse. The CGI-I has been used as a measure in previous clinical psychopharmacology trials and will be completed by the study physician and clinician at each visit based upon clinical observations. It is a clinician rated global measure of improvement that will be completed at baseline, weeks 2 through 8 and at follow-up. It takes about 5 minutes.

**Salivary Oxytocin Levels:** Saliva will be collected by means of an Oragene-Discover collection kit (ORG-500). If able, subjects will spit saliva directly into the collection tube. If the child is unable to spit into the tube, we will use Oragene's OG-AC1 assisted collection swabs to collect saliva from the inside subject's cheeks. Samples will be collected pre-dose and one-hour post-dose at baseline, week 4 and week 8. A salivary sample will also be taken at the follow up visit. It takes approximately 10 minutes to complete.

*Justification for Measurement of Salivary Levels:* We have selected salivary measures of OXT, since Gordon et al [73] demonstrated that salivary OXT levels are directly correlated with brain activity and enhancements in brain function. After administration of IN-OXT, levels of salivary OXT increase markedly and have been shown to remain elevated for up to 7 hours after administration vs. placebo. In fact, low doses (16 IU OXT) did not show weaker effects and tended to elevate the initial salivary OXT compared to higher doses (24 IU). Salivary OXT levels on placebo were highly correlated over time, indicating individual stability of OXT levels. Another study [100], utilized a double-blind placebo-control within-subject design. Ten subjects

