Measurements obtained at a specific time point (e.g. 8 weeks) will be compared between the IN-OXT and placebo groups with the two sample t-test or Wilcoxon rank sum test. In addition, the change in outcome measures between baseline and 8 weeks will be compared between

treatment groups. Exploratory analyses will first be performed to evaluate whether the magnitude of changes in these variables between the two time points depends on the baseline value. If there is no evidence that change is dependent on baseline, then two sample tests will be used to compare the mean change in each variable between treatment groups; otherwise, analysis of covariance models will be fit to the data where the outcome is the level measured at 8 weeks, and the main effects are treatment group and baseline value [15;37]. Adjustment for any patient characteristics which appear to be imbalanced across treatment groups will be accomplished by including the relevant terms as additional covariates into the model. To compare longitudinal trends in outcomes between treatment groups, linear mixed effects models will be fit to all repeated measures obtained during follow-up, with main effects for time and treatment group and a time x treatment interaction term; this is a widely used statistical approach in longitudinal studies of psychiatric outcomes. Appropriate data transformations, such as the log transform, will be applied if the data deviate from the normal distribution. Although a number of different outcomes will be analyzed, we will not adjust for multiple testing given the exploratory nature of this study.

Additional subgroup analyses will also be performed to evaluate and compare treatment effects in males and females. Given the limited sample size of this Phase 2 trial, however, any subgroup analyses will be viewed as exploratory.

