#### **Detailed Description of Analyses**

**Primary Analyses**: Analyses for Specific Aim (1): To compare IN-OXT vs. placebo with respect to improvement in the hyperphagia severity in children with PWS via improvement in scores on the Hyperphagia Questionnaire-Clinical Trials.

The primary analysis will evaluate the hypothesis that IN-OXT will decrease hyperphagia vs. placebo.

- 1. Response to treatment will be assessed in two ways:
  - a. The effects of IN-OXT on hyperphagia will be analyzed using an intent-totreat approach with the two-sample T-test or Wilcoxon rank sum tests to compare treatment groups at specific visits as well as linear mixed effects models to analyze the repeated measures and changes over time.
  - b. The proportion of responders in each treatment group will also be compared. Response will be defined as a 30% or greater decrease in food-seeking and eating behaviors from baseline on the Hyperphagia Questionnaire-Clinical Trials. Dropouts for clinical reasons will be coded as non- responders. Differences in the proportion of responders in each treatment group will be evaluated using the chi-square test and time to response will be assessed using survival analytic techniques.
  - c. All tests will be two-tailed with an alpha level of 0.05.

**Secondary Analyses:** Analyses for Specific Aims (2) through (8): To compare IN-OXT vs. placebo in children with PWS on change in:(2) Repetitive behaviors via scores on the Repetitive Behavior Scale – Revised (RBS-R) and Montefiore-Einstein Rigidity Scale-Revised (MERS-PWS)(3) Weight and body composition via impedance analysis. (4) Quality of Life Measures on the World Health Organization Quality of Life Scale (WHOQOL)(5) Clinical Global Impression Scale (CGI-I) (6) Salivary Oxytocin Concentration (7) Safety Analyses

IN-OXT and placebo groups will be compared to the above secondary measures will be analyzed using methods similar to those outlined above. Associations between outcome measures at a specific time point will be analyzed with the Spearman rank or Pearson correlation coefficient.

- 1. Secondary Aim (1) Repetitive Behaviors
  - *a.* The effects of treatment on frequency and severity of repetitive behaviors will be assessed by fitting linear mixed effects models to the data on the RBS-R scores. We hypothesize that IN- OXT will significantly reduce repetitive behaviors from baseline to endpoint compared to Placebo.

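### The mixed model takes in the post-treatment week-10 visit and names no week-8 contrast, although the objective is change from baseline to week 8

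*Combined protocol and SAP*

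**What the plan says.** The primary aim (Specific Aims) is to compare the groups on "changes on the Hyperphagia Questionnaire-Clinical Trials (HQ-CT) from baseline to week 8 in children with PWS". The Research Strategy describes an "8-week treatment trial of IN-OXT vs. placebo in 50 child and adolescent subjects", and the Schedule of Events (Table 2) marks treatment at baseline, week 4 and week 8 but not at week 10. Week 10 is therefore a post-treatment visit.

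The protocol calls that visit follow-up: "Visits at screening, weeks 2, 4, 6, and 10 (follow-up) are remote visits". The CGI-I description uses the word in the same way: "will be completed at baseline, weeks 2 through 8 and at follow-up". On the primary measure, "The HQ-CT will be administered at screening, baseline, and at all subsequent visits", and Table 2 marks HQ-CT at week 10.

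The Summary of Analytic Approach introduces the mixed model with the words "To compare longitudinal trends in outcomes between treatment groups". It states that "linear mixed effects models will be fit to all repeated measures obtained during follow-up, with main effects for time and treatment group", and adds a time-by-treatment interaction. It does not say whether time is continuous or categorical, sets no last visit, and names no contrast at a given visit. Under Primary Analyses the model stands beside the two-sample tests: "linear mixed effects models to analyze the repeated measures and changes over time". Under Secondary Aim 1 it is the only method named for RBS-R and MERS-PWS.

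The same summary separately plans a week-8 two-sample comparison and a comparison of change to week 8, with ANCOVA on the week-8 value if change depends on baseline.

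**The concern.** The interaction is the model's only treatment comparison over time, and as written it is not a week-8 effect. If time is linear, one slope is fitted across on-treatment and post-treatment visits, so an effect that fades after treatment pulls the slope difference towards zero. If time is categorical, the joint interaction test asks whether the group profiles differ anywhere, week 10 included.

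The model could therefore understate a real week-8 benefit or react to a difference present only after treatment. This matters because the model is part of the primary analysis, the plan does not say which primary result decides, and the missing-data section relies on it to handle data missing at random.

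**Working it through.** **The plan's own figure.** The Power Analysis gives 25 per group, d = 0.8, two-sided 5%, two-sample t-test, 80% power. The noncentrality is 0.8/√(2/25) = 2.83. Power is 80.7% by the normal approximation and 79.1% by noncentral t on 48 df, so the figure is reproduced.

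**Assumptions not in the documents.** Equal variances at all visits, correlation 0.5 between visits, complete data, baseline in the outcome vector, and a week-8 effect of 0.8 SD. At correlation 0.5 the SD of change equals the SD of the score. Two profiles y of the treatment difference are used, as fractions of the week-8 effect: early (full from week 2) and linear build-up. The early profile fits the Titration Schedule's remark that initial response was seen at weeks 1 and 2. The fraction r remaining at week 10 is set at 1, 0.5 or 0, since the documents give no figure.

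**Linear time.** With S = Σ(t − t̄)y and Sxx = Σ(t − t̄)², the interaction scaled to 8 weeks, per unit of week-8 effect, is 8S/Sxx. The noncentrality is (0.8·S/Sxx)/√((2/25)·0.5/Sxx) = 4S/√Sxx, on 48 df.

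For HQ-CT at weeks 0, 2, 4, 6, 8 and 10, t̄ = 5 and Sxx = 70. Through week 8, t̄ = 4 and Sxx = 40.

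| Profile | Visits | S | 8S/Sxx | 4S/√Sxx | Power |
|---|---|---|---|---|---|
| Early | to week 8 | 4 | 0.80 | 2.53 | 70% |
| Early | week 10, r = 1 | 5 | 0.57 | 2.39 | 65% |
| Early | week 10, r = 0.5 | 2.5 | 0.29 | 1.20 | 22% |
| Early | week 10, r = 0 | 0 | 0.00 | 0.00 | 5% |
| Build-up | to week 8 | 5 | 1.00 | 3.16 | 87% |
| Build-up | week 10, r = 1 | 7.5 | 0.86 | 3.59 | 94% |
| Build-up | week 10, r = 0.5 | 5 | 0.57 | 2.39 | 65% |
| Build-up | week 10, r = 0 | 2.5 | 0.29 | 1.20 | 22% |

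For the early profile, the step from 1.00 to 0.80 comes from linear time itself; only the further drop comes from week 10.

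For MERS-PWS (weeks 0, 4, 8, 10; Sxx = 59), the early profile (full from week 4) gives 0.75, 0.44 and 0.14, with power 80%, 38% and 8%. Build-up gives 0.85, 0.54 and 0.24, with power 89%, 53% and 15%. Without week 10 both give 1.00 and 79%.

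*Sensitivity.* Over correlations 0.3 to 0.7 the early HQ-CT power is 51–86%, 17–33% and 5%, against 55–89% without week 10. With first-order autoregressive correlation (0.8 per two weeks) and r = 0, the scaled interaction is 0.00 (early) and 0.03 (build-up).

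**Categorical time, joint interaction test.** Noncentrality = 12.5 × 0.64 × Σ(y − ȳ)²/0.5, on 5 and 240 df (4 and 192 through week 8).

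- Early: 13.33, 14.00 and 21.33 for r = 1, 0.5 and 0, so power is 81%, 83% and 96% (82% through week 8).
- Build-up: 13.33, 10.00 and 13.33, so power is 81%, 67% and 81% (70% through week 8).
- With unstructured covariance the range is 62–94%.
- If the groups differ only at week 10 (an illustration, not a profile the documents suggest), the noncentrality is 3.33 at 0.4 SD and 13.33 at 0.8 SD, and the test rejects 24% and 81% of the time.

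**Named week-8 contrast, week 10 kept as its own category.** Week 8 minus baseline has noncentrality 0.8/√(2/25 × 2 × 0.5) = 2.83 in every profile. Power is 79% on 48 df and 80% on 240 df. In simulation (20,000 trials per profile) it was 80–81% in all six profiles, and 5% when the groups differed only at week 10.

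**The separate planned tests.** The week-8 change t-test has 79% power. ANCOVA has noncentrality 0.8/√(2/25 × (1 − 0.5²)) = 3.27 and 89% power. Neither depends on week 10.

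**The case against.** The strongest reply has four parts.

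1. The Outcome Measures paragraph ties outcomes to week 8, the RBS-R and MERS-PWS hypotheses run to endpoint, and the missing-data section calls this an 8-week trial. This fixes the target but gives the model no last visit and no contrast.
2. Follow-up in the model sentence must be generic, since one visit is not a set of repeated measures. Granted, but the generic sense covers everything after baseline and so still includes week 10.
3. The model is there to compare trends, while other tests answer the week-8 question, for the secondary scales too through the general strategy. This stands, and it limits the point to one model. It does not explain why a trend in the primary efficacy analysis should run past the end of treatment.
4. The harm depends on assumptions. This is largely true. Material power loss needs linear time and a fading effect; with build-up and full retention, week 10 raises power from 87% to 94%. With categorical time it moves joint power by −4 to +14 points.

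A further objection is that the figures put baseline in the outcome vector, whereas the sentence could mean post-baseline visits only. That reading does not help. For an early, fully retained effect over weeks 2 to 10 the profile is flat, so S = 0 and the slope difference is 0.00 (through week 8 as well). With half retained, S = −2 and Sxx = 40, so the scaled slope is −0.40, the wrong sign.

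**Conclusion.** The concern holds, for the mixed model only. By its plain wording the model includes post-treatment data, and nothing in it estimates the week-8 difference that the objective asks for. The plan does contain valid week-8 tests, and its stated power, which is for a t-test, is correct.

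The size depends on what the documents leave open. Under linear time the HQ-CT interaction recovers from 0.00 to 0.86 of the week-8 effect, with power between 5% and 94%; the serious losses occur only if the effect fades by week 10. Under categorical time power is largely kept, and the fault lies in what is tested. In a small Phase 2 trial this is a moderate point, but it should be settled before unblinding, so that the time coding and the use of week 10 are not chosen after results are seen.

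**What to change.** For the efficacy mixed model, state in the SAP that visit is categorical, that baseline score is included, and that the treatment difference at week 8 is the model's estimate and test. Then either restrict the model to visits through week 8, or keep week 10 as its own category outside the efficacy test. Report week 10 separately as post-treatment data. Apply the same wording to RBS-R and MERS-PWS.

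As a separate minor point, reconcile the RBS-R schedule: its description under Secondary Outcome Measures lists baseline and weeks 4 and 8, while Table 2 also marks week 10. Until then it is unclear whether the RBS-R model has week-10 data.

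The cost is SAP wording and a few degrees of freedom for categorical visit. No new data, visits, patients or software are needed.

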#### **Detailed Description of Analyses**

**Primary Analyses**: Analyses for Specific Aim (1): To compare IN-OXT vs. placebo with respect to improvement in the hyperphagia severity in children with PWS via improvement in scores on the Hyperphagia Questionnaire-Clinical Trials.

The primary analysis will evaluate the hypothesis that IN-OXT will decrease hyperphagia vs. placebo.

- 1. Response to treatment will be assessed in two ways:
  - a. The effects of IN-OXT on hyperphagia will be analyzed using an intent-totreat approach with the two-sample T-test or Wilcoxon rank sum tests to compare treatment groups at specific visits as well as linear mixed effects models to analyze the repeated measures and changes over time.
  - b. The proportion of responders in each treatment group will also be compared. Response will be defined as a 30% or greater decrease in food-seeking and eating behaviors from baseline on the Hyperphagia Questionnaire-Clinical Trials. Dropouts for clinical reasons will be coded as non- responders. Differences in the proportion of responders in each treatment group will be evaluated using the chi-square test and time to response will be assessed using survival analytic techniques.
  - c. All tests will be two-tailed with an alpha level of 0.05.

**Secondary Analyses:** Analyses for Specific Aims (2) through (8): To compare IN-OXT vs. placebo in children with PWS on change in:(2) Repetitive behaviors via scores on the Repetitive Behavior Scale – Revised (RBS-R) and Montefiore-Einstein Rigidity Scale-Revised (MERS-PWS)(3) Weight and body composition via impedance analysis. (4) Quality of Life Measures on the World Health Organization Quality of Life Scale (WHOQOL)(5) Clinical Global Impression Scale (CGI-I) (6) Salivary Oxytocin Concentration (7) Safety Analyses

IN-OXT and placebo groups will be compared to the above secondary measures will be analyzed using methods similar to those outlined above. Associations between outcome measures at a specific time point will be analyzed with the Spearman rank or Pearson correlation coefficient.

- 1. Secondary Aim (1) Repetitive Behaviors
  - *a.* The effects of treatment on frequency and severity of repetitive behaviors will be assessed by fitting linear mixed effects models to the data on the RBS-R scores. We hypothesize that IN- OXT will significantly reduce repetitive behaviors from baseline to endpoint compared to Placebo.
  - *b.* The effects of treatment on frequency and severity of repetitive behaviors will be assessed by fitting linear mixed effects models to the data on the MERS-PWS scores. We hypothesize that IN- OXT will significantly reduce repetitive behaviors from baseline to endpoint compared to Placebo.
- 2. Secondary Aim (2) Weight, BMI (z-score) and body composition via bioelectrical impedance analysis
  - a. Weight and BMI (z-score) will be measured at each visit. It will be utilized to evaluate whether IN-OXT significantly modulates energy metabolism and reduces weight compared to placebo. Body composition via impedance analysis will be measured at baseline and endpoint.
- 3. Secondary Aim (3) Quality of Life Measures
  - a. The relationship between quality of life and treatment will be assessed using scores on the WHOQOL. We hypothesize that IN-OXT will improve quality of life from baseline to endpoint as measured by an increase in overall score on the WHOQOL from when compared to placebo.
  - b. The relationship between caregiver strain and treatment will be assessed using scores on the CSQ. We hypothesize that IN-OXT will caregiver strain from baseline to endpoint as measured by an reduction in overall score on the WHOQOL from when compared to placebo.
- 4. Secondary Aim (4) Salivary Oxytocin Levels
  - a. Both group and individual differences in salivary OXT concentration will be measured. Correlations between individual salivary OXT concentrations at day 1 and weeks 4 and 8 as well as correlations between OXT and changes in our primary outcome measure, hyperphagia assessed by the [name] Hyperphagia Questionnaire, will be evaluated using the Spearman rank or Pearson correlation. Additional correlation analysis will be performed on salivary oxytocin levels and secondary outcome measures: RBS-R, WHOQOL and CGI-I. We hypothesize that higher concentrations of salivary oxytocin will be correlated with positive changes on each outcome measure, indicating improvement in symptoms.
- 5. Secondary Aim (5) Safety Analyses
  - a. Rates of specific side effects and other adverse events will be tabulated and compared between treatment groups using the chi-square test. Please see the section labeled "Safety Analyses" for further details on how adverse events will be monitored and rated.
  - b. The relationship between frequency of suicidal behaviors will be assessed on the ABC-I to evaluate whether IN-OXT vs. placebo is associated with a change in the irritability subscale of the ABC-I which serves as a surrogate for suicidal ideation in this population.

